# 9.3 Blinding and Unblinding Procedures

In order to maintain the study blind the randomization schedule will be generated by a third party. Randomization will be performed according to a computer-generated randomization scheme. The placebo and tablets for all strengths of AS012 look alike which ensures blinding. The Investigational Product will be provided in identically labeled and packaged such that neither the Subject nor any Investigator can identify the treatment. The Drug Labeling, Packaging and Shipping facility will hold the randomization code throughout the conduct of the study in order to minimize bias. A sealed copy of the randomization scheme (as a scratch off portion of the product label attached to the drug accountability page) will be retained at the study site. In the event of an emergency, the Subject-specific treatment may be identified; however, every effort should be made to maintain the blind. Where possible, the Medical Monitor should be contacted before breaking the blind for any subject. The Sponsor must be notified in the event the blind is broken.

The treatment assignments will remain blinded until the final database is closed.

May 20, 2022 Protocol: **AS012-20-01** Page 49 of 88

If Suspected Unexpected Serious Adverse Reactions (SUSAR) requires unblinding by a Regulatory Agency, a designated member of the Sponsor's safety team will be un-blinded on case-by-case basis by receiving the randomization directly from the study unblinded statistical consultant.

The bioanalytical team will analyse the samples collected from all subjects, including samples from subjects assigned to placebo to ease the selection of samples and avoid releasing the randomization code.

### 9.4 Significance Level

Tests for superiority over placebo for the primary and the key secondary end-point will be conducted via a straight step-down approach in the order of highest to lowest dose to preserve the overall Type I error rate of 0.05.

# 9.5 Datasets to be Analyzed

Three analysis populations will be used in the analysis of the clinical data:

- 1. A Safety Population subject is any individual who was randomized into the study and dispensed study drug.
- 2. The ITT Population includes all randomized subjects regardless of whether they received the investigational product.

Additionally, the Screen Fail subjects will be summarized, including reasons for removal.

## 9.6 Demographics and Baseline/Randomization Characteristics

Demographic and baseline/randomization characteristics will be summarized descriptively by treatment group for the ITT, and Safety Populations.

### 9.7 Safety Assessment

Safety Assessments will include vital signs, physical examination, adverse events (AEs), laboratory tests, ECG monitoring, chest X-ray (if not done in last 6 months) and Columbia-Suicide Severity Rating Scale (C-SSRS).

The safety of AS012 will be evaluated by:

- o Incidence, seriousness and severity of all adverse events
- Shifts from baseline in hematology and laboratory tests
- Change from baseline in ECG parameters; Frequencies and percentages of ECG findings

The extent of exposure will be summarized using descriptive statistics. No inferential analyses are planned.

Incidence of all adverse events reported during the study will be summarized using the Medical Dictionary For Regulatory Activities (MedDRA) dictionary by System Organ Class and Preferred Term, by treatment group, severity, and relationship to study drug.

An AE is considered treatment emergent if it was not present prior to the first dose of treatment or, if it was present, it worsened in severity or treatment attribution.

Safety analyses will be performed on the Safety Population. All safety data will be listed by treatment and subject in data listings. AEs will also be summarized by actual dose at time of onset of the AE to account for possible dose reductions over the course of the study.

May 20, 2022 Protocol: **AS012-20-01** Page 50 of 88

# 9.8 Efficacy Assessment

# **Primary endpoints:**

• Mean change, from baseline, in VASI score at Week 24

[figure not shown]
# Key Secondary endpoint:

· Mean change, from baseline, in VES at Week 24.

[figure not shown]

Mean change, from baseline, in VIPs at Week 24

# Other Secondary endpoints:

May 20, 2022 Protocol: **AS012-20-01** Page 51 of 88

May 20, 2022 Protocol: **AS012-20-01** Page 52 of 88

### Efficacy Analysis

The primary efficacy endpoint will be evaluated using the Intent-to-Treat (ITT) Population. The primary endpoint method of analysis will use an Analysis of Covariance (ANCOVA) model to compare change from baseline in VASI score results between treatment arms at Week 24. The ANCOVA model will include fixed effects for treatment, stability of disease (stable vs. non-stable),

baseline VASI score as a covariate. Point estimates and 95% confidence intervals will be obtained for the difference between each active dose versus placebo.

Missing VASI data at Week 24 will be addressed in the model using multiple imputation methods.

Secondary efficacy variables will be analyzed similarly, however without using multiple imputation methods.

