4.2 Key secondary endpoints

Key secondary endpoints of this study are:

- Change from baseline in VES at Week 24.
- Change from baseline in VIPs at Week 24

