5.2 Intent-to-Treat (ITT) Population

The Intent-to-Treat (ITT) Population will consist of all randomized subjects regardless of whether they received the investigational product. This population will be the main population for the efficacy analyses. Subjects will be analyzed according to the treatment they were randomized to receive.

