6.9 Efficacy Analyses

6.9.1 Analysis of the primary endpoint

6.9.1.1 Imputation of the primary endpoint

VASI total score will be calculated as explained in Appendix IV to the protocol. Missing Week 24 assessments of VASI will be imputed using multiple imputations methods. For each subject in the ITT population with missing endpoint 50 imputations will be performed using Fully Conditional Specifications (FCS) predictive mean matching imputation model with the factors of the primary analysis model (i.e., treatment, stability of disease [stable vs. non-stable at screening], and baseline VASI score as a covariate,) and VASI score at Week 12. Each imputed dataset will be analyzed as described in the next section. The results will be combined using Rubin's rule. See Section 11.2.1 for detailed description of the imputation procedure and SAS sample code.

[figure not shown]

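### VES and VIPs at Week 24 are analysed without imputation, so if drop-out follows Week 12 worsening their estimates can be biased towards no effect, and by more than the primary

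*Protocol*

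**What the plan says.** Protocol 9.8 (Efficacy Analysis) treats the primary endpoint and the rest differently. For the primary: "Missing VASI data at Week 24 will be addressed in the model using multiple imputation methods". For the others: "Secondary efficacy variables will be analyzed similarly, however without using multiple imputation methods". The synopsis repeats both statements.

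SAP 4.2 names the key secondary endpoints: "Change from baseline in VES at Week 24" and "Change from baseline in VIPs at Week 24".

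SAP 6.9.1.1 gives the primary 50 imputations by FCS predictive mean matching, using the factors of the analysis model "and VASI score at Week 12". The code is in SAP 11.2.1. The placebo-based sensitivity code in SAP 11.2.2 is headed for the primary endpoint only.

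Of the ITT population (all randomised subjects), SAP 5.2 says: "This population will be the main population for the efficacy analyses".

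Protocol 9.2 plans for about 20% drop-out. Protocol Section 3 lets the investigator discontinue a subject as a treatment failure when the condition has worsened, with a VASI rise of 25% or more as the example. Section 4.6 lists worsening among the reasons for removal.

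Protocol Section 3 and 7.15 also ask sites to try to hold a visit at or near Week 24 for subjects who leave before Visit 7, to collect the focused area assessments. In Protocol 7.7, VES is in that group, while VIPs is listed as subject-reported.

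**The concern.** An ANCOVA without imputation uses only subjects who have a Week 24 value. It is unbiased if, given treatment and the baseline covariates, being missing is unrelated to the outcome. The protocol itself names a way in which that could fail: subjects may leave because their vitiligo has worsened. If worsening is commoner on placebo, as it would be under the planned effect, deleting those subjects makes placebo look better and shrinks the estimated difference.

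The primary analysis is partly protected because its imputation model sees Week 12 VASI. The key secondaries are not. VASI and VES results could then diverge because of missing-data handling rather than because of the endpoints. In a dose-ranging trial these estimates would inform the choice of dose even if no formal test rests on them.

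**Working it through.** **Inputs from the documents (Protocol 9.2, SAP 3.2).** Week 24 VASI change is -5.50 on AS012 and -1.56 on placebo, a difference of 3.94. SD of change is 6.4, baseline mean 15.7, baseline SD 8.9, drop-out about 20%, with 52 evaluable per arm. Neither document gives a mean, SD, correlation or drop-out rate by arm for VES or VIPs, so the check uses the VASI scale as an illustration.

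**The plan's own figure.** n per arm = 2 × (1.960 + 1.036)² × (6.4/3.94)² = 47.4, so 48. At 52 per arm the power is 88%, not 85%. The stated 52 is reached if the interim look described in SAP 3.2 is included (O'Brien-Fleming-type spending at 75% information, read as efficacy plus non-binding futility): 47.4 × 1.095 = 51.9. The standard error of a difference at 52 per arm is 6.4 × √(2/52) = 1.26.

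**Simulation.** One million subjects in two equal arms, with these assumptions:
- mean Week 12 change is half the Week 24 change, with SD 0.8 × 6.4
- the correlation between Week 12 and Week 24 change within arm is 0.5 or 0.8
- total drop-out is 20%, either random or logistic in the standardised change, with slope 1 or 2 per SD

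Three estimators were compared: complete-case ANCOVA, imputation from the model covariates alone, and imputation that adds Week 12 change. Imputation was taken at its large-sample limit (regression prediction).

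| Drop-out driven by | Slope | Correlation | Drop-out placebo / active | Complete case | With Week 12 | Gap |
|---|---|---|---|---|---|---|
| Nothing (random) | – | 0.5 | 20% / 20% | 3.93 | 3.93 | 0.00 |
| Nothing (random) | – | 0.8 | 20% / 20% | 3.94 | 3.94 | 0.00 |
| Week 12 change | 1 | 0.5 | 22.7% / 17.4% | 3.82 | 3.95 | 0.13 |
| Week 12 change | 1 | 0.8 | 22.5% / 17.3% | 3.73 | 3.93 | 0.20 |
| Week 12 change | 2 | 0.5 | 24.0% / 16.0% | 3.64 | 3.94 | 0.29 |
| Week 12 change | 2 | 0.8 | 24.0% / 16.1% | 3.48 | 3.94 | 0.47 |
| Unseen Week 24 change | 1 | 0.5 | 24.0% / 15.9% | 3.52 | 3.61 | 0.10 |
| Unseen Week 24 change | 1 | 0.8 | 24.1% / 15.9% | 3.53 | 3.77 | 0.25 |
| Unseen Week 24 change | 2 | 0.5 | 26.1% / 13.8% | 3.04 | 3.22 | 0.18 |
| Unseen Week 24 change | 2 | 0.8 | 26.2% / 13.8% | 3.02 | 3.54 | 0.53 |

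Gaps are taken before rounding.

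**What this shows.**
- In every row, imputation from the model covariates alone gave the complete-case answer. The gain comes from the post-baseline predictor, not from imputing as such.
- When drop-out follows Week 12 worsening, complete cases are 0.13 to 0.47 below Week 12 imputation, or 0.1 to 0.4 standard errors. The gap falls roughly in proportion to the correlation (0.29 against 0.47 for 0.5 against 0.8).
- When drop-out follows unseen worsening, Week 12 imputation still misses 3.94 by 0.17 to 0.72.
- In the least favourable Week 12 row, an estimate centred on 3.48 instead of 3.94 would take power at 52 per arm from 88% to about 79% (3.48/1.26 - 1.96 = 0.81).

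**Extreme bound.** Suppose every subject with a Week 24 rise above 0.25 × 15.7 = 3.93 points were deleted. The fractions removed are 1 - Φ((3.93 + 1.56)/6.4) = 19.6% on placebo and 1 - Φ((3.93 + 5.50)/6.4) = 7.0% on active. The remaining means are -3.76 and -6.43, a difference of 2.67. The plan does not prescribe this, because the discontinuation is discretionary.

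**The case against.** A reader might infer that everyone who drops out after worsening is deleted, that a fifth of the randomised subjects are lost, and that the key secondary results are therefore more biased than the primary. The documents do not support that.

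- **Retrieval.** Sites are asked to obtain focused area assessments near Week 24 after early discontinuation, and VES is one of them. So 20% is a planning drop-out rate, not the rate of missing VES. This stands, with limits. The wording does not cover VIPs. SAP 3.1 leaves the retrieval visit out. SAP 6.1 restricts by-visit summaries to scheduled visits, and no visible rule assigns a retrieved value to Week 24.
- **The bias is conditional.** Discontinuation for worsening is optional, the 25% rise is only an example, and Protocol 4.6 lists many other reasons. If drop-out depends only on treatment and baseline covariates, there is no extra bias. If it depends on unseen values, the primary is biased too. This stands.
- **Direction.** The bias shown is towards no effect, so it does not manufacture a positive finding. This stands.
- **Inferential role.** Protocol 9.4 sets out a step-down for "Tests for superiority over placebo for the primary and the key secondary end-point", but SAP 6.1.2 makes all p-values beyond the primary nominal, with no inference drawn. The point cannot rest on 0.05 protection until the two agree.
- **SAP detail.** The SAP text on continuous secondary endpoints is not legible in the public copy, so other handling there cannot be ruled out. The protocol rule is nonetheless explicit and stated twice.

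**Conclusion.** The point holds as a conditional one. The protocol rules out multiple imputation for VES and VIPs, so subjects with no Week 24 value leave an analysis whose main population is all randomised subjects. If drop-out follows worsening already visible in Week 12 VASI, the estimates can be biased towards no effect, and by more than the primary.

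On the VASI planning scale, complete cases then give 3.48 to 3.82 (3% to 12% below 3.94), against 3.93 to 3.95 with Week 12 imputation. This rests on assumed 20% drop-out, logistic drop-out slopes of 1 to 2 per SD and correlations of 0.5 to 0.8. The figures are not estimates for VES or VIPs, and the gap shrinks as correlation with VASI weakens. VIPs is the more likely of the two to be missing, because retrieval does not cover it, but nothing in the documents shows how closely it tracks VASI. In no simulated setting was Week 12 imputation materially worse than complete cases. That is the argument for changing a stated rule at little cost, even though the size of the bias is unknown.

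**What to change.** In the SAP, and in Protocol 9.8 where it states the rule:

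1. Analyse VES and VIPs at Week 24 with 50-fold FCS imputation, combined by Rubin's rule. Use the primary-model factors, the endpoint's own baseline, and VASI change at Week 12 as auxiliary variable. Add Week 24 VASI change where it is observed. That helps mainly VIPs, since VES and VASI are collected together.
2. Do not use End of Study VASI as a predictor. For early leavers it is timed at drop-out, and completers have no counterpart.
3. State that Week 24 values from retrieved visits enter the analysis.
4. Keep the complete-case ANCOVA as a sensitivity analysis. The other secondary endpoints can stay as planned.

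The cost is a little more programming and an imputation model that crosses endpoints, because no Week 12 VES or VIPs is visible in the schedule. No new data are needed. It should be settled before the Week 24 unblinding.

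Separately, reconcile Protocol 9.4 (key secondary in the step-down) with SAP 6.1.2 (nominal p-values, no inference).

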## Sensitivity Analyses

Sensitivity analyses will be included to investigate the impact of missingness, and will include a completer analysis without imputation, as well as imputation based on placebo scores. Type I error (alpha,  $\alpha$ ) will be preserved in the primary efficacy analysis by use of a closed test step-down approach. Beginning with the highest dose, pairwise comparisons to placebo will be made until a non-significant result at the alpha ( $\alpha$ ) 0.05 level is reached, at which time testing will stop.

# Interim Analysis (IA)

No formal Interim Analysis will be performed for this study.

Part I analysis will include all safety and efficacy assessments conducted at week 24. Analysis outputs will be generated when the last subject has completed 24 weeks of study participation, and may include results for all available visits/data. After Part I database lock, subject-level unblinded information will be confined to a designated unblinded study team. A separate document/SAP will provide further details related to unblinding of personnel. A designated list of blinded and unblinded study personnel shall be maintained. Part I analysis subject-level data will not be provided to the site staff and the blinded study team.

An additional unblinded analysis could be undertaken at a subsequent time (e.g. after last patient completed week 36/52 visit) by the unblinded study team to assess the efficacy if required based on the sponsor's discretion. If such an analysis is planned to be undertaken the details would be discussed in SAP.

### Final Analysis

The final study database will be locked following last patient last visit at Week 64, once all subject data have been cleaned and all coding of terms (AE, Concomitant Medications, Medical History) has been finalized. Investigational sites, subjects, and study team members directly involved in study activities will remain blinded to study treatment assignments until the database lock. The unblinded subject-level data will be provided to the PI at the end of the study.

### 9.9 Concomitant Medication

The start and stop date of concomitant medication use during the study will be provided in the data listings in addition to the reason for the medication use.

### 9.10 Summary of Subjects who terminate prematurely

Reasons for premature termination will be summarized by treatment group.

May 20, 2022 Protocol: **AS012-20-01** Page 53 of 88

### 10. ADVERSE EVENTS

### 10.1 Reporting of Adverse Events

Any untoward medical occurrence in a Subject or clinical-trial Subject administered a medicinal product and which does not necessarily have to have a causal relationship with this treatment. An adverse event can therefore be any unfavorable and unintended sign, symptom, or disease temporally associated with the use of a medicinal product, whether or not considered related to the medicinal product.

Any adverse event associated with the use of a drug in humans, whether or not considered product-related, including the following: An adverse event occurring in the course of the use of a drug product in professional practice; an adverse event occurring from drug overdose whether accidental or intentional; an adverse event occurring from drug abuse; an adverse event occurring from drug withdrawal; and any failure of expected pharmacological action. Reporting an adverse event does not necessarily reflect a conclusion that the product caused or contributed to the adverse event.

All adverse events, whether observed by an Investigator or Study Coordinator or reported by the Subject, whether related to study drug or not related to study drug, shall be documented in the Subject records, together with details, i.e., date of onset, description of the AE, the duration and intensity of each episode, the action taken, the relationship to the Investigational Product and the degree of severity, the seriousness, date of resolution, and the outcome.

In the completed and on-going studies for AS012, based on the safety data review, no safety signals were noted till date.

The Principal Investigator must strive to follow the Subject until the adverse event has resolved, becomes clinically insignificant, is stabilized or the Subject is lost to follow-up. The Principal Investigator must immediately report to the Contract Research Organization, by telephone and follow-up in writing, all study drug discontinuations due to adverse events.

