### Clinical Evaluations will be performed at:

```
Visit 1: Screening Visit (Week ≥ -4 / Day -28 to -1);
Visit 2: Baseline Visit (Week 1 / Day 1);
Visit 3: Interim Visit (Week 4 / Day 29 ± 3 Days);
Visit 4: Interim Visit (Week 12 / Day 85 ± 3 Days);
Visit 5: Interim Visit (Week 16 / Day 113 ± 3 Days);
Visit 6: Interim Visit (Week 20 / Day 141 ± 3 Days);
Visit 7: Interim Visit (Week 24 / Day 169 ± 3 Days);
Visit 8: Interim Visit (Week 28 / Day 197 ± 3 Days);
Visit 9: Interim Visit (Week 36 / Day 253 ± 3 Days);
Visit 10: Interim Visit (Week 44 / Day 309 ± 3 Days);
Visit 11: Interim Visit (Week 48 / Day 337 ± 3 Days);
Visit 12: End of Treatment Visit (Week 52 / Day 365 ± 3 Days);
Visit 13: Follow-up Visit (Week 64 / Day 449 ± 3 Days);
```

Subjects will be admitted into the study after informed consent has been obtained. An Unscheduled Visit is allowed at any time, for any reason, if in the Principal Investigator's opinion it is warranted. If a Subject is discontinued from the study during an Unscheduled Visit, the Unscheduled Visit will be referred to as an Early Discontinuation Visit. For all the subjects who discontinue the study prior to Visit 7 all efforts should be made to conduct a visit at, or close to week 24 to collect focused area assessments. Regardless of the reason, subjects discontinued from IP prior to the end of study will be required to complete the End of Study (EoS) assessment within 2 weeks after the last dose.

[figure not shown]
Randomization and re-randomization will be stratified by stability of disease (stable vs. non-stable)

The assigned Investigational Product will be administered orally three tablets three times a day, in the morning, in the afternoon, and in the evening according to a randomization scheme. Subjects will be required to use diaries to document the date of study treatments, any missed treatments and the occurrence of all adverse events.

[figure not shown]
The duration of each Subject's participation in the study will be approximately 64 weeks (449 days).

If the Principal Investigator determines that the Subject's condition has worsened to the degree that it is unsafe for the Subject to continue in the study (e.g. an increase in VASI score from baseline by  $\geq 25\%$ ), the Subject may be discontinued from the study as a treatment failure and the Subject may be treated using the standard care.

May 20, 2022 Protocol: **AS012-20-01** Page 20 of 88

May 20, 2022 Protocol: **AS012-20-01** Page 21 of 88

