## 5.7 Adverse Events (AEs)

Any AEs reported after signing Informed Consent should be reported. An adverse event is defined as any untoward medical occurrence (sign, symptom or abnormal laboratory finding) regardless of severity in a Subject or clinical-trial Subject administered a medicinal product and which does not necessarily have to have a causal relationship with this treatment. All adverse events, whether observed by an Investigator or Study Coordinator or reported by the Subject, whether related to study drug or not related to study drug, shall be documented on Subject records, together with details, i.e. date of onset, description of the AE, the duration and intensity of each episode, the action taken, the relationship to the investigational product and the degree of severity, the seriousness, date of resolution, and the outcome.

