#### 6 STUDY EVALUATIONS

### 6.1 Efficacy

Efficacy assessments should be performed by the investigator or a designee who is appropriately trained and experienced in the assessment of vitiligo patients.

PGA, assessment assessment should be done (in the listed order) by the investigator before performing other efficacy assessments and after obtaining the subject questionnaires.

Subjects who worsen beyond their scores at baseline will be described in the safety evaluation.

The inter-rater reliability and validity for VASI, and VES will be performed at Baseline and at EoT by approximately 5 sites with approximately 50 subjects.

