### The following procedures will be performed at Baseline:

- 4. Compliance with the inclusion and exclusion criteria, including results of laboratory evaluations and chest X-ray will be reviewed.
- A medical history will be updated with any changes of the Subject's health since the previous study visit. (See Section 5.1)
- 6. A urine pregnancy test will be conducted for all females of childbearing potential (see Section 5.4)
- After confirming the eligibility, the Subject will be randomized and assigned a number using Interactive Response Technology (IRT). (see Section 8.5)
- 8. The use of concomitant medications since the previous study visit will be documented and assessed. (See Section 5.6)
- 9. The Subject's diary provided at the previous visit will be collected and reviewed.
- Vital signs (blood pressure, pulse, respiratory rate and oral body temperature) will be documented. Subjects must remain in a seated or supine position for at least 5 minutes before vital signs are obtained. (See Section 5.3)
- 11. A blood sample(s) will be collected for Hematology, Chemistry, Coagulation profile and Lipid Profile (Coagulation profile and Lipid Profile need not be repeated at baseline if these assessments for screening visit are performed within 2 weeks prior to the Visit 2) (See Section 5.5)

- 15. Subjects will be instructed to take the study drug with approximately 240 mL (8 oz.) of water. Tablets should be swallowed intact and not chewed or crushed. (See Section 8.6)
- 16. The occurrence of all AEs will be assessed and documented following the procedures in Sections 5.7, 10.1, and 10.3.
- 17. A query for Columbia-Suicide Severity Rating Scale (C-SSRS) will be performed (See Section 5.8)

Vitiligo Impact Patient Scale (VIPs)

- 20. Focused Area Assessments will be performed for:
  - Physician Global Assessment (PGA)
  - Vitiligo Area and Scoring Index (VASI) will be evaluated. To be included in the study, subjects must have vitiligo with VASI score 4 or higher

    At designated sites VASI will be performed by two independent assessors to test reliability and validity

May 20, 2022 Protocol: **AS012-20-01** Page 36 of 88

- Vitiligo Extent Score (VES) will be evaluated.
- 21. The following will be dispensed:
  - The IP kit assigned for Visit 2 by IRT
  - A diary card with instructions and to record health changes and concomitant medication

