6.11.1 Adverse Events

Adverse Events will be coded using the MedDRA (Version 23.1) AE coding system for purposes of summarization.

[figure not shown]
An AE will be considered as treatment-emergent (TEAE) if the date of onset is on or after the date of the first study drug administration. AEs with unknown start dates will be counted as treatment-emergent unless the AE resolution date is prior to the study drug start date. If the start date is partially missing, the AE will be considered treatment-emergent, unless the month and year (when available) rule out the possibility that the event occurred post start of study drug dosing.

A TEAE is defined as treatment-related if its relationship to study medication is recorded as "Possible", "Probable" or "Definite" on the eCRF. In case the relatedness was not assessed, the most conservative result (related) will be chosen for the analysis.

For subjects initially randomized to Placebo and later re-randomized to AS012 AEs will be assigned to either Placebo or AS012 treatment based on the date of onset, i.e., AEs that start prior to the first dose of AS012 will be assigned to the Placebo treatment and AEs that start on or after the date of the first AS012 dose will be assigned to the AS012 treatment.

TEAEs will be defined as occurring in Part I of the study if the date of onset is prior to the date of the subject's Week 24 visit. For subjects who discontinue prior to Week 24 visits, all their TEAEs will be defined as occurring in Part I. AEs starting on or after the date of the subject's Week 24 visit will be defined as occurring after Part I.

All summaries of TEAEs will be presented in three ways:

In summaries of TEAEs a subject experiencing the same AE multiple times on the same treatment will only be counted once for that preferred term and treatment. Similarly, if a subject experiences multiple AEs within the same system organ class on the same treatment that subject will be counted only once in that system organ class and treatment. When summarizing AEs by severity, only the most severe occurrence within the preferred term or system organ class and treatment will be used. Similarly, when summarizing AEs by

relationship to study drug, only the most related occurrence within the preferred term or system organ class and treatment will be selected for displays in summary tables.

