An overall summary for the Safety population will include, by treatment and overall, the number and percentage of subjects reporting at least 1 TEAE in the following categories:

- Any TEAE
- Treatment-related TEAE
- Serious TEAE
- Treatment-related serious TEAE
- TEAE leading to discontinuation of the study medication
- Treatment-related TEAE leading to discontinuation of the study medication
- TEAE requiring temporary interruption of study medication
- Treatment-related TEAE requiring temporary interruption of study medication
- TEAE leading to death.

The following TEAE frequency tables will be prepared summarizing the overall number of TEAEs, the number and percentage of subjects reporting at least one TEAE by MedDRA System Organ Class (SOC) and preferred term (PT), by treatment group for the Safety population:

- All TEAEs
- Serious TEAEs
- Treatment-related TEAEs
- AEs leading to discontinuation of the study medication
- TEAEs by Severity
- TEAEs by Relationship to Study Drug.

Overall summary of TEAEs and the summary of TEAEs by SOC and PT will be presented separately for TEAEs occurring in Part I, occurring after Part I and for all TEAEs for subjects initially randomized to AS012 treatment.

All information pertaining to AEs noted during the study will be listed by subject, detailing verbatim, preferred term, system organ class, start date, stop date, intensity, outcome, action taken and causal relationship to the study drug. The AE onset will also be shown relative (in number of days) to the date of first administration of the study drug. In addition the AE duration (if AE Stop Date is available) will be evaluated as below and presented (in number of days).

AE Duration = AE Stop Date - AE Start Date + 1

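### Protocol 10.1 counts failure of drug action as an adverse event and 5.7 does not, so vitiligo non-response can enter the aggregate TEAE rows under no stated rule

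*Protocol*

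**What the plan says.** Protocol 5.7 defines an adverse event as "any untoward medical occurrence (sign, symptom or abnormal laboratory finding) regardless of severity". Section 10.1 opens in similar terms. Its second paragraph then adds a list covering overdose and abuse and closing with "an adverse event occurring from drug withdrawal; and any failure of expected pharmacological action".

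The Section 7 visit lists cite the two sections together. At Baseline, for example: "The occurrence of all AEs will be assessed and documented following the procedures in Sections 5.7, 10.1, and 10.3".

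Worsening of vitiligo is mentioned in other places:

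- Protocol 6.1: "Subjects who worsen beyond their scores at baseline will be described in the safety evaluation".
- Protocol Section 3: where the investigator judges continuation unsafe, with a VASI rise of at least 25% as the example, "the Subject may be discontinued from the study as a treatment failure". This is not called an AE.
- Protocol 4.6 lists worsening and adverse events as separate reasons for removal.
- Protocol 5.10, on treatment interruption for AEs, groups the same VASI rise with allergic and other drug reactions.

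SAP 6.11.1 classes an AE as "treatment-emergent (TEAE) if the date of onset is on or after the date of the first study drug administration". Its overview gives "the number and percentage of subjects reporting at least 1 TEAE in the following categories", including any, treatment-related and discontinuation TEAEs. AEs are assigned to the treatment at onset (SAP 6.1.1 and 6.11.1).

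**The concern.** In a placebo-controlled trial whose outcome is repigmentation, failure of the expected drug action is ordinary non-response. The protocol never says whether non-response or worsening is to be recorded as an AE, and the two definitions that govern the same entry disagree about it. Recording could therefore differ between sites.

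Events recorded this way are efficacy outcomes. Once inside the any-TEAE, treatment-related or discontinuation rows, they carry the treatment effect into the safety comparison. In a dose-ranging study, TEAE rates by dose are a main safety output. With no inferential safety analysis planned (Protocol 9.7), readers will judge these raw percentages by eye.

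**Working it through.** **Wording.** Protocol 10.1 includes failure of action and 5.7 does not. Both apply at each visit. The visible SAP rule depends on onset date alone. Nothing visible removes non-response from the TEAE count, so an investigator who follows 10.1 to the letter creates TEAEs out of non-response.

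**Inputs.** The documents state no TEAE rate, so there is no plan figure to reproduce. The planning inputs (Protocol 9.2, SAP 3.2) are:

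- mean VASI improvement at Week 24: 1.56 on placebo, 5.50 on AS012
- SD of change: 6.4
- about 64 subjects in each of five arms, one placebo and four AS012

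Assumptions that are not in the documents:

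- change is normally distributed and every AS012 dose reaches 5.50
- b, the rate of other TEAEs, is equal across arms
- r, the chance that a worsened subject is recorded as an AE, is equal across arms and independent of other TEAEs
- the Week 24 distribution stands in for events dated within Part I

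**Share with any worsening**, Φ(−mean/SD):

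- placebo: Φ(−1.56/6.4) = Φ(−0.244) = 0.404
- AS012: Φ(−5.50/6.4) = Φ(−0.859) = 0.195
- difference: 20.9 points

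With an SD of 5 the shares are 0.378 and 0.136; with 8.9 they are 0.430 and 0.268.

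**Effect on the any-TEAE row.** Each subject counts once, so an arm's rate is 1 − (1 − b)(1 − r·p). The added placebo-minus-AS012 difference is (1 − b) × r × (0.404 − 0.195):

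| b | r = 0.10 | r = 0.50 | r = 1 |
|---|---|---|---|
| 0.3 | 1.5 points | 7.3 | 14.6 |
| 0.5 | 1.0 | 5.2 | 10.4 |
| 0.7 | 0.6 | 3.1 | 6.3 |

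If AS012 has no effect, the added difference is zero.

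**Counts.** 64 × 0.404 = 25.8 on placebo, and 256 × 0.195 = 49.9 across the four AS012 arms. Placebo holds 25.8/75.7 = 34% of the worsened subjects (29% to 41% over the SD range).

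**After Week 24.** Continuing placebo subjects are re-randomised to AS012, so later events can fall only on AS012. Dating matters too. SAP 6.11.1 places an AE starting on the Week 24 visit date after Part I, and one starting on the day of the first AS012 dose under AS012. Protocol 8.6 has a supervised dose at that visit. A placebo subject's non-response dated to that visit would then count against AS012.

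**The case against.** The strongest opposing case is that the disputed clause is generic. It sits among items such as professional practice, overdose and abuse, and nothing shows that sites would read it as an instruction to record VASI non-response. The protocol has its own label for serious worsening, and reasons for premature termination are summarised separately. That stands as a reason to expect r to be well below 1. It does not remove the contradiction, because no sentence tells a site which reading applies.

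A reader might infer that these events fall mostly on placebo and so make AS012 look safer. The documents do not support that. The excess is in the per-arm rate, in Part I, and only if AS012 works. By count about two thirds fall on AS012, and after Week 24 the direction reverses.

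A reader might also infer that a true AS012 excess of 13 to 24 points could be cancelled. Those figures are differences in the efficacy events alone:

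- worse by at least 3.925 (25% of the mean baseline of 15.7): 19.6% vs 7.0%
- improved by less than 3.925: 64.4% vs 40.3%

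They apply one threshold to every subject instead of 25% of each subject's own baseline. No document makes under 25% improvement a failure of action. In the any-TEAE row they shrink to about 6 to 12 points at b = 0.5, even with full reporting.

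Three further objections stand:

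- Worsening, as distinct from non-response, could pass as an untoward sign under 5.7, so 10.1 is not the only route.
- Tables by preferred term would show these terms on their own lines; only the aggregate rows blur.
- The list of the three TEAE presentations in SAP 6.11.1 is not visible and the shells are separate, so an exclusion or a worsening table may exist there.

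**Conclusion.** The inconsistency is real and should be resolved. Protocol 5.7 and 10.1 disagree on failure of action, both bind sites, and no visible SAP rule keeps non-response out of the TEAE counts. Under the planning assumptions and a 50% background rate, the any-TEAE difference in Part I shifts by roughly 1, 5 or 10 points towards a higher placebo rate at 10%, 50% or 100% reporting. Reporting and background rates are assumptions, and the shift disappears for an ineffective dose. Over the whole study the direction is not fixed. Because safety is descriptive and preferred terms are tabulated, the harm is a blurred comparison that depends on site practice, not a false test result or a hidden signal.

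**What to change.** 1. Reconcile Protocol 5.7 and 10.1 to one AE definition. Either delete the failure-of-action clause from 10.1, or state that non-response alone is captured by VASI and PGA and is not counted as a TEAE. Tell sites in a short memo.
2. In SAP 6.11, summarise by arm the number and percentage of subjects with VASI above baseline, separately from TEAEs. This delivers the description that Protocol 6.1 announces and keeps worsening visible in the safety evaluation.
3. For data already collected, show the TEAE overview with and without lack-of-efficacy and vitiligo preferred terms.

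If the table shells already contain items 2 or 3, a cross-reference in the SAP is enough. The cost is a clause, a memo and one or two tables from data already held. The downside is slightly lower TEAE rates.
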